6.2.1.1 Ribociclib

Recommendations for dose reduction, interruption or discontinuation of ribociclib in the management of study drug related adverse reactions are summarized in [Table 6-3](#), [Table 6-4](#), [Table 6-5](#) and [Table 6-6](#).

Clinical judgment of the treating physician should guide the management plan of each patient based on individual benefit/risk assessment. However, for events requiring a discontinuation in [Table 6-3](#), [Table 6-4](#), [Table 6-5](#) and [Table 6-6](#) or listed in Section 7.1, treatment must be discontinued.

If a patient inadvertently doses ribociclib on a rest day (e.g. days 22-28 of any given cycle), ribociclib should be interrupted to ensure 7 consecutive rest days and avoid overdose. The visit schedule will not be adjusted.

Table 6-3 Ribociclib dose adjustment and management recommendations for hematological adverse reactions

Toxicity/Grade	Dose Adjustment and Management Recommendations
Thrombocytopenia	
Grade 1($\geq 75 \times 10^9/L$)	No dose adjustment required.
Grade 2 ($\geq 50 \times 10^9/L - < 75 \times 10^9/L$)	Dose interruption until recovery to grade ≤ 1 . Re-initiate ribociclib at the same dose.
Grade 3 ($\geq 25 \times 10^9/L - < 50 \times 10^9/L$)	Dose interruption until recovery to grade ≤ 1 . Re-initiate ribociclib at the same dose level. If toxicity recurs at grade 3: temporary dose interruption until recovery to grade ≤ 1 and reduce ribociclib to the next lower dose level.
Grade 4($< 25 \times 10^9/L$)	Dose interruption until recovery to grade ≤ 1 . Re-initiate ribociclib at the next lower dose level. If toxicity recurs at grade 4: discontinue ribociclib
Absolute neutrophil count (ANC),	
Grade 1 ($\geq 1.5 \times 10^9/L$)	No dose adjustment required.
Grade 2 ($\geq 1.0 - < 1.5 \times 10^9/L$)	No dose adjustment required.

Toxicity/Grade	Dose Adjustment and Management Recommendations

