Grade 3 (< 8.0 g/dL)	Dose interruption until recovery to grade ≤ 2 . Re-initiate ribociclib at the same dose.
Grade 4 Life-threatening consequences; urgent intervention indicated	Discontinue ribociclib.

Table 6-4 **Ribociclib dose adjustment and management recommendation for hepatic toxicities**

HEPATOTOXICITY (BILIRUBIN, SGPT/ALT, SGOT/AST)	
TOTAL BILIRUBIN without ALT/AST increase above baseline value	
Grade 1 (> ULN – 1.5 x ULN) (confirmed 48-72h later)	Maintain dose level with LFTs monitored bi-weekly
Grade 2 (> 1.5 – 3.0 x ULN)	
Dose interruption of ribociclib
 
If resolved to ≤ grade 1 in ≤ 21 days, then maintain dose level
 
If resolved to ≤ grade 1 in > 21 days or toxicity recurs, then reduce 1 dose level
 
Repeat liver enzyme and bilirubin tests twice weekly for 2 weeks after dose resumption
 
If toxicity recurs after two dose reductions, discontinue ribociclib

Grade 3 (> 3.0 – 10.0 x ULN)	
Dose interruption of ribociclib
 
If resolved to ≤ grade 1 in ≤ 21 days, lower 1 dose level of ribociclib
 
Repeat liver enzyme and bilirubin tests twice weekly for 2 weeks after dose resumption
 
If resolved to ≤ grade 1 in > 21 days or toxicity recurs, discontinue ribociclib

Grade 4 (> 10.0 x ULN)	Discontinue ribociclib
Confounding factors and/or alternative causes for increase of total bilirubin should be excluded before dose interruption/reduction. They include but are not limited to: evidence of obstruction, such as elevated ALP and GGT typical of gall bladder or bile duct disease, hyperbilirubinemia due to the indirect component only (i.e. direct bilirubin component ≤ 1 x ULN) due to hemolysis or Gilbert Syndrome, pharmacologic treatment, viral hepatitis, alcoholic or autoimmune hepatitis, other hepatotoxic drugs. For patients with Gilbert Syndrome, these dose modifications apply to changes in direct bilirubin only. Bilirubin will be fractionated if elevated.	
AST or ALT	
AST or ALT without bilirubin elevation > 2 x ULN	
Same grade as baseline or increase from baseline grade 0 to grade 1 (confirmed 48 – 72 h later)	No dose adjustment required with LFTs monitored per protocol if same grade as baseline or bi-weekly in case of increase from baseline grade 0 to 1

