Increase from baseline grade 0 or 1 to grade 2 (> 3.0 – 5.0 x ULN)	
Dose interruption of ribociclib
 
If resolved to ≤ baseline grade in ≤ 21 days, then maintain dose level
 
If resolved to ≤ baseline grade in > 21 days or toxicity recurs, then reduce 1 dose level
 
Repeat liver enzyme and bilirubin tests twice weekly for 2 weeks after dose resumption
 
If toxicity recurs after two dose reductions or recovery to ≤ baseline grade is > 28 days, discontinue ribociclib

Increase from baseline grade 0 or 1 to grade 3 (> 5.0 – 20.0 x ULN)	
Dose interruption of ribociclib until resolved to ≤ baseline grade, then lower 1 dose level of ribociclib
 
Repeat liver enzyme and bilirubin tests twice weekly for 2 weeks after dose resumption
 
If recovery to ≤ baseline grade is > 28 days, discontinue ribociclib
 
If toxicity recurs, discontinue ribociclib

Increase from baseline grade 2 to grade 3 (> 5.0 – 20.0 x ULN)	
Dose interruption of ribociclib until resolved to ≤ baseline grade, then lower 1 dose level of ribociclib
 
Repeat liver enzyme and bilirubin tests twice weekly for 2 weeks after dose resumption

	If toxicity recurs after two dose reductions or recovery to \leq baseline grade is > 28 days, discontinue ribociclib.
Grade 4 ($> 20.0 \times$ ULN)	Discontinue ribociclib
AST or ALT and concurrent Bilirubin	
For patients with normal ALT and AST and total bilirubin at baseline: AST or ALT $> 3.0 \times$ ULN combined with total bilirubin $> 2 \times$ ULN without evidence of cholestasis Or For patient with elevated AST or ALT or total bilirubin at baseline: baseline: [AST or ALT $> 2 \times$ baseline AND $> 3.0 \times$ ULN] OR [AST or ALT $8.0 \times$ ULN]- whichever is lower- combined with [total bilirubin $> 2 \times$ baseline AND $> 2.0 \times$ ULN]	Discontinue ribociclib
Confounding factors and/or alternative causes for increased transaminases should be excluded before dose interruption/reduction. They include but are not limited to: concomitant medications, herbal preparations or dietary supplements, infection, hepato-biliary disorder or obstruction, new or progressive liver metastasis, and alcohol intake.	

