6.2.1.2 Additional follow-up for hepatic toxicities

Increase in transaminases combined with total bilirubin (TBIL) increase may be indicative of drug-induced liver injury (DILI), and should be considered as clinically important events. A study with ribociclib in non-cancer patients with varying degrees of hepatic impairment (mild, moderate, severe based on Child-Pugh classification) matched subjects with normal hepatic function was completed (CLEE011A2109). Refer to [Ribociclib Investigators Brochure] for more details.

The threshold for potential DILI may depend on the patient's baseline AST/ALT and TBIL value; patients meeting any of the following criteria will require further follow-up as outlined below:

- For patients with normal ALT and AST and TBIL value at baseline: AST or ALT $> 3.0 \times$ ULN combined with TBIL $> 2.0 \times$ ULN
- For patients with elevated AST or ALT or TBIL value at baseline: [AST or ALT $> 2 \times$ baseline AND $> 3.0 \times$ ULN] OR [AST or ALT $> 8.0 \times$ ULN], whichever is lower, combined with [TBIL $> 2 \times$ baseline AND $> 2.0 \times$ ULN]

Medical review needs to ensure that liver test elevations are not caused by cholestasis, defined as: ALP elevation $> 2.0 \times$ ULN with R value < 2 in patients without bone metastasis, or elevation of ALP liver fraction in patients with bone metastasis.

Note: The R value is calculated by dividing the ALT by the ALP, using multiples of the ULN for both values. It denotes the relative pattern of ALT and/or ALP elevation is due to cholestatic or hepatocellular liver injury or mixed type injury).

In the absence of cholestasis, these patients should be immediately discontinued from study drug treatment, and repeat LFT testing as soon as possible, preferably within 48 hours from the awareness of the abnormal results. The evaluation should include

laboratory tests, detailed history, physical assessment and the possibility of liver metastasis or new liver lesions, obstructions/compressions, etc.

Hepatic toxicity monitoring includes the following LFTs: albumin, ALT, AST, total bilirubin, direct and indirect bilirubin, alkaline phosphatase (fractionated if alkaline phosphatase is grade 2 or higher), creatine kinase (CK), prothrombin time (PT)/INR and GGT. For patients with Gilbert Syndrome: total and direct bilirubin must be monitored, intensified monitoring applies to changes in direct bilirubin only.

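### Table 6-4 gives a weaker action, or no row at all, for joint bilirubin and ALT/AST rises that fall short of the concurrent-elevation row

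*Protocol*

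**What the plan says.** Table 6-4 (Protocol 6.2.1.1) manages hepatic toxicity in three blocks.

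- **Bilirubin block**, headed "TOTAL BILIRUBIN without ALT/AST increase above baseline value". Grade 1 (up to 1.5 x ULN): keep the dose, bi-weekly liver tests. Grade 2 (above 1.5, up to 3.0): interrupt. Grade 3 (above 3.0, up to 10.0): interrupt, then one level lower. Grade 4: discontinue. Grades 2 and 3 carry a 21-day recovery limit, which for grade 3 reads "grade 1 in > 21 days or toxicity recurs, discontinue ribociclib", and a fixed retest rule: "Repeat liver enzyme and bilirubin tests twice weekly for 2 weeks after dose resumption".
- **ALT/AST block**, headed "AST or ALT without bilirubin elevation > 2 x ULN". The lowest row (same grade as baseline, or grade 0 to 1) begins "No dose adjustment required with LFTs monitored per protocol if same grade as baseline or bi-weekly in case of increase from baseline". Interruption starts with a rise to grade 2 (above 3.0 x ULN).
- **Concurrent block**: discontinue. A normal baseline needs ALT/AST above 3 x ULN and bilirubin above 2 x ULN, without cholestasis. An elevated baseline needs ALT/AST above twice baseline and above 3 x ULN, or 8 x ULN, whichever is lower, with bilirubin above twice baseline and above 2 x ULN.

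Section 6.2.1.2 repeats the concurrent cut-offs. Section 6.2.1.1 adds that "Clinical judgment of the treating physician should guide the management plan of each patient", but makes the tables' discontinuations mandatory. Table 6-6 (6.2.1.4) covers all other adverse reactions.

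**The concern.** The headings do not tile. Any ALT/AST value above baseline closes the bilirubin rows, and bilirubin above 2 x ULN closes the ALT/AST rows. A joint rise below the concurrent threshold therefore meets either the lowest ALT/AST row alone or nothing. In the first situation the hepatic table prescribes less for a worse liver picture. In the second it loses its own recovery limit and post-restart tests. Hepatobiliary toxicity is one of three important identified risks in 1.2.6, and 6.2.1.2 itself treats a combined transaminase and bilirubin rise as a possible sign of drug-induced liver injury.

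**Working it through.** There is no plan figure to reproduce. The check is a literal lookup of Table 6-4. Values are in multiples of ULN and are illustrative. Baseline bilirubin is taken as 0.8, there is no cholestasis, and other causes are assumed excluded. Where ALT is unchanged, the bilirubin row is taken as governing.

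**Concurrent threshold for ALT/AST.** Normal baseline: 3.0. Elevated baseline b: min(max(2b, 3), 8).

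- b = 1.5: 2b = 3.0, threshold 3.0
- b = 2.4: 2b = 4.8, threshold 4.8
- b = 3.5: 2b = 7.0, threshold 7.0
- b = 4.5: 2b = 9.0, capped at 8.0

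Inclusion criterion 11 admits ALT below 2.5 x ULN, or below 5 x ULN with liver metastasis, so all four baselines can occur.

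**(a) Bilirubin above 1.5 and up to 2.0 x ULN**

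| Baseline ALT | ALT now | Bilirubin | Matching row | Action |
|---|---|---|---|---|
| 0.8 | 0.8 | 1.8 | Bilirubin grade 2 | Interrupt |
| 0.8 | 2.0 | 1.8 | ALT grade 0 to 1 only | Dose unchanged, bi-weekly tests |
| 1.5 | 1.5 | 1.8 | Bilirubin grade 2 | Interrupt |
| 1.5 | 2.5 | 1.8 | ALT same grade only | Dose unchanged, tests per protocol |
| 0.8 | 4.0 | 1.8 | ALT grade 2 | Interrupt |

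The second and fourth lines are the inversion. In the fourth, tests per protocol means Day 1 of each 28-day cycle from cycle 3 (7.2.2.4.2), whereas isolated grade 1 bilirubin (for example 1.3) gets bi-weekly tests. The last line shows that a rise to ALT grade 2 is not affected.

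**(b) Bilirubin above 2 x ULN**

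| Baseline ALT | ALT now | Bilirubin | Matching row | Action |
|---|---|---|---|---|
| 0.8 | 0.8 | 4 | Bilirubin grade 3 | Interrupt |
| 0.8 | 2.0 or 3.0 | 4 | None | – |
| 0.8 | 3.1 | 4 | Concurrent | Discontinue |
| 2.4 | 4.5 | 4 | None | – |
| 2.4 | 4.9 | 4 | Concurrent | Discontinue |
| 4.5 | 7.5 | 4 | None | – |
| 4.5 | 8.1 | 4 | Concurrent | Discontinue |

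Section 6.2.1.2 does not fill the gap, because its cut-offs are the same.

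**What is lost in (b) if Table 6-6 is used instead.** Start from 600 mg. Sections 6.1.2 and 6.6 stop treatment after an interruption of more than 4 weeks, so the tables can differ only between the 21-day limit and day 28: 28 − 21 = 7 days.

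| Bilirubin grade | Recovery | Table 6-4 | Table 6-6 |
|---|---|---|---|
| 2 | By day 21 | Restart 600 mg | Restart 600 mg |
| 2 | Days 22–28 | Restart 400 mg | Restart 600 mg |
| 3 | By day 21 | Restart 400 mg | Restart 400 mg |
| 3 | Days 22–28 | Discontinue | Restart 400 mg |
| 4 | – | Discontinue | Discontinue |

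The fixed retests after restart (2 per week x 2 weeks = 4) also go. A stricter recurrence rule at grade 3 is lost only if recurrence in Table 6-4 means recurrence at any grade; Table 6-6 discontinues at grade 3.

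**The case against.** The strongest reply is that Table 6-4 should not be read alone. In (a) the ALT row grades only ALT/AST, so the bilirubin event can itself be called unlisted and sent to Table 6-6, which interrupts at grade 2. Interruption then brings close observation two or three times weekly (6.2.1.2), follow-up at least weekly for 28 days or until the event resolves or stabilises (6.6), and weekly biochemistry until baseline or grade 1 (7.2.2.4.2). Apart from discontinuations, the tables are recommendations under clinical judgment, and a row that requires no adjustment does not forbid one.

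Most of this stands and lowers the severity. A reader might infer that sites are obliged to continue 600 mg in (a), or that (b) is unmanaged; the documents support neither. A reader might also take ALT 7.5 with bilirubin 4 at baseline ALT 4.5 as the worst case. Yet for the ALT rise Table 6-6 grade 3 gives an action equal to or stricter than the ALT row that applies at bilirubin 1.9: interrupt, require recovery to grade 1 rather than to baseline grade, restart one level lower, and discontinue on a grade 3 recurrence.

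What does not fall is the inversion inside the hepatic table. Nothing says that Table 6-6 takes over when a hepatic row matches and says to leave the dose alone, and the extra testing rules start only once an interruption or dose change is called for.

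**Conclusion.** The fault is confirmed on the printed text, within limits. It covers joint rises below the concurrent threshold: (a) bilirubin above 1.5 and up to 2.0 x ULN with ALT/AST above baseline but only grade 1; and (b) bilirubin above 2 x ULN with ALT/AST above baseline and not above 3 x ULN (normal baseline) or the baseline-relative limit, at most 8 x ULN. It does not cover every joint rise. Those meeting the concurrent row are discontinued, and a rise to ALT/AST grade 2 or higher with bilirubin at or below 2 x ULN is at least interrupted.

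In (a) the size is interruption against unchanged dosing in the matching row. In (b) it is one dose step or a mandatory stop for recovery on days 22 to 28, and four fixed retests. The conclusion assumes literal use of the headings and elevations judged drug-related.

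The number of patients affected cannot be derived. A reader might scale up the four Hy's Law cases among 334 ribociclib patients in the pivotal phase III trial (1.2.6), but patients of that kind reach the concurrent row and are already discontinued, so the count does not measure this gap.

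This is a minor safety-table correction. Amendment 4 states that enrollment is complete, so it matters only for patients still on treatment. In the pivotal trial 31 of 37 (83.8%) grade 3/4 ALT/AST rises came in the first six months (7.2.2.4.2), which suggests lower remaining risk.

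**What to change.** Reword the heading of the bilirubin block to: *Total bilirubin elevation not meeting the concurrent ALT/AST-plus-bilirubin criteria.* Add one sentence: *If a bilirubin row and an ALT/AST row both match, the stricter action applies.*

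Check with a normal baseline: ALT 2.5 with bilirubin 1.8 then gives interruption. ALT 2.5 with bilirubin 2.5, 5 and 12 gives interruption, interruption with a lower dose, and discontinuation.

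Do not change the cholestasis wording at the same time. The branch beginning "For patient with elevated AST or ALT or total bilirubin at baseline" carries no cholestasis exception, whereas 6.2.1.2 says "In the absence of cholestasis, these patients should be immediately discontinued from study drug treatment" for both baseline groups. The table is the stricter text and a site can obey both. Adding the exception to that branch would relax a mandatory discontinuation.

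The cost is one heading, one sentence and a site notification. A few more patients will be interrupted and will have the retests that the table already contains. No new type of test is needed.

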6.2.1.2 Additional follow-up for hepatic toxicities

Increase in transaminases combined with total bilirubin (TBIL) increase may be indicative of drug-induced liver injury (DILI), and should be considered as clinically important events. A study with ribociclib in non-cancer patients with varying degrees of hepatic impairment (mild, moderate, severe based on Child-Pugh classification) matched subjects with normal hepatic function was completed (CLEE011A2109). Refer to [Ribociclib Investigators Brochure] for more details.

The threshold for potential DILI may depend on the patient's baseline AST/ALT and TBIL value; patients meeting any of the following criteria will require further follow-up as outlined below:

- For patients with normal ALT and AST and TBIL value at baseline: AST or ALT $> 3.0 \times$ ULN combined with TBIL $> 2.0 \times$ ULN
- For patients with elevated AST or ALT or TBIL value at baseline: [AST or ALT $> 2 \times$ baseline AND $> 3.0 \times$ ULN] OR [AST or ALT $> 8.0 \times$ ULN], whichever is lower, combined with [TBIL $> 2 \times$ baseline AND $> 2.0 \times$ ULN]

Medical review needs to ensure that liver test elevations are not caused by cholestasis, defined as: ALP elevation $> 2.0 \times$ ULN with R value < 2 in patients without bone metastasis, or elevation of ALP liver fraction in patients with bone metastasis.

Note: The R value is calculated by dividing the ALT by the ALP, using multiples of the ULN for both values. It denotes the relative pattern of ALT and/or ALP elevation is due to cholestatic or hepatocellular liver injury or mixed type injury).

In the absence of cholestasis, these patients should be immediately discontinued from study drug treatment, and repeat LFT testing as soon as possible, preferably within 48 hours from the awareness of the abnormal results. The evaluation should include

laboratory tests, detailed history, physical assessment and the possibility of liver metastasis or new liver lesions, obstructions/compressions, etc.

Hepatic toxicity monitoring includes the following LFTs: albumin, ALT, AST, total bilirubin, direct and indirect bilirubin, alkaline phosphatase (fractionated if alkaline phosphatase is grade 2 or higher), creatine kinase (CK), prothrombin time (PT)/INR and GGT. For patients with Gilbert Syndrome: total and direct bilirubin must be monitored, intensified monitoring applies to changes in direct bilirubin only.

Close observation is recommended in case of AST, ALT, and/or bilirubin increase requiring dose interruption, which involves:

- Repeating liver enzyme and serum bilirubin tests **two or three times weekly**. Frequency of re-testing can decrease to once a week or less if abnormalities stabilize or return to normal values.
- Obtaining a more detailed history of current symptoms.
- Obtaining a more detailed history of prior and/or concurrent diseases, including history of any pre-existing liver conditions or risk factors.
- Obtaining a history of concomitant drug use (including non-prescription medications, herbal and dietary supplements), alcohol use, recreational drug use, and special diets.
- Ruling out acute viral hepatitis types A, B, C, D, and E; hepatotropic virus infections (CMV, EBV or HSV); autoimmune or alcoholic hepatitis; NASH; hypoxic/ischemic hepatopathy; and biliary tract disease.
- Obtaining a history of exposure to environmental chemical agents.
- Obtaining additional tests to evaluate liver function, as appropriate (e.g., INR, direct bilirubin).
- Considering gastroenterology or hepatology consultations.
- Assessing cardiovascular dysfunction or impaired liver oxygenation, including hypotension or right heart failure as possible etiologies for liver dysfunction.
- Liver biopsy as clinically indicated to assess pathological change and degree of potential liver injury.

All cases confirmed on repeat testing meeting the laboratory criteria defined above, with no other alternative cause for LFT abnormalities identified, should be considered as “medically significant”, thus met the definition of SAE (Section 8.2.1), and reported as SAE using the term “potential drug-induced liver injury”. All events should be followed up with the outcome clearly documented.

6.2.1.3 Additional follow-up for QTc prolongation

Table 6-5 Ribociclib dose adjustment and management recommendation for QTc prolongation (CTC AE v4.03)

Grade	Dose Modification
For All Grades	
1. Check the quality of the ECG and the QT value and repeat if needed.2. Perform analysis of serum electrolytes (K+, Ca++, Phos, Mg++). If outside of the normal range, interrupt ribociclib administration, correct with supplements or appropriate therapy as soon as possible, and repeat electrolytes until documented as normal.3. Review concomitant medication usage for the potential to inhibit CYP3A4 and/or to prolong the QT interval.4. Check compliance with correct dose and administration of ribociclib. 
Consider collecting a time matched PK sample; record date and time of last study drug intake.

1 QTcF 450-480 ms	Perform steps 1-4 as directed in "For All Grades". No dose adjustment required.
2 QTcF 481-500 ms	
Interrupt ribociclib. Perform steps 1-4 as directed in "For All Grades."
 
Perform a repeat ECG within one hour of the first QTcF of ≥ 481 ms. Repeat ECG as clinically indicated until the QTcF returns to < 481 ms, restart LEE011 with dose reduced by 1 dose level.
 
If QTcF ≥ 481 ms recurs, ribociclib should be reduced by 1 dose level. Repeat ECGs 7 days and 14 days after dose resumption (then as clinically indicated) for any patients who had therapy interrupted due to QTcF ≥ 481 ms.

3 QTcF ≥ 501 ms on at least two separate ECGs	
Interrupt ribociclib. Perform steps 1-4 as directed in "For All Grades."
 
Transmit ECG immediately and confirm prolongation/abnormalities.
 
Perform a repeat ECG within one hour of the first QTcF of ≥ 501 ms.
 
If QTcF remains ≥ 501 ms, consult with a cardiologist (or qualified specialist) and repeat cardiac monitoring as indicated until the QTcF returns to < 481 ms.
 
If QTcF returns to < 481 ms, ribociclib will be reduced by 1 dose level.
 
If QTcF remains ≥ 481 ms after performing steps 1-4 as directed in "For All Grades," discontinue LEE011.
 
Repeat ECGs 7 days and 14 days after dose resumption (then as clinically indicated) for any patients who had therapy interrupted due to QTcF ≥ 501 ms.
 
If QTcF of ≥ 501 ms recurs, discontinue ribociclib.

4 [QT/QTcF ≥ 501 or > 60 ms change from baseline] and [Torsades de pointes or polymorphic ventricular tachycardia, or signs/symptoms of serious arrhythmia]	
Discontinue ribociclib. Perform steps 1-4 as directed in "For All Grades."
 
• Obtain local cardiologist (or qualified specialist) consultation and repeat cardiac monitoring as indicated until the QTcF returns to < 481 ms.

